3.9 DATA COLLECTION PROCEDURE

The qualitative data will be collected through FGD and in-depth interviews of the students and a simulation exercise. Interviews will be done using an interview guide until we reach a point of saturation. Each interview will last about 30 minutes.

Quantitative data will be collected on **three** first aid variables: first aid knowledge, practical skills, and helping behaviour (attitude) using pre and posttest questionnaires composed of multiple-choice questions. This will be done using an adapted evidence-based pretested tool called “Stop the Bleed” Education Assessment Tool (SBEAT)[20] in adaptation with the LFRs training tools.

3.10 DATA MANAGEMENT AND ANALYSIS

Quantitative data will be collected using interview-administered questionnaires in Kobo collect, then stored in coded excel sheets to be analyzed using R software.

Qualitative data will be transcribed and coded into transcripts to be analyzed using codes in Atlasti.

3.11 DATA ANALYSIS PLAN

A difference-in-difference analysis would be done to assess the change in KAPs before and after the intervention in. The posttest would be done immediately after the 4 days of training for each pool and 3 months after the training to assess the need for refresher course planning.

The exposure variables include training on LTBs from injury first aid and the use of these services by the trained students (e.g., the number of persons assisted or referred during the follow-up period of the training).

We will analyze survey data using R Software with a combination of descriptive statistics and parametric and non-parametric tests to establish statistically significant differences between pre- and post-test results and between the intervention and control groups.

Table 7: Objectives and their Indicators

Objective	Activities/process	Data collection tools	Data Source	Indicators
1. To understand the perspectives of stakeholders on YoFA training program among SSC	- In-depth interviews	-In-depth interview guides	School teachers, administrators, parents, community leaders and students	
2. To assess school children's KAP (willingness and self-efficacy on trauma/injury FA via the built YoFA training to stop LTBs.	- survey	-Questionnaire	- students	- Obtain baseline KAP Scores
3. To evaluate the effectiveness and usability of the YoFA training program for SSC to respond to LTBs safely and promptly in their environs.	-Training following a specific STB and LFRs program -Training students on specific modules of LTB FA - Pre and post test -Simulation exercises	- Use adapted tools from the SBEAT - Questionnaires - Evaluation form with questions how? What was the situation?where, and how?	Stakeholders, teachers, parents, students	- Change in knowledge scores -At least 50% of stakeholders rate the program as good/ expectations met - 70% of students rate the program as good/expectations met - Number of children who made use of the FA skills taught
4. To determine the barriers associated with implementing the YoFA program among early SSC in the Fako Division.	- Interviews - Survey	-Interview guides - Questionnaires	- Stakeholders, - Teachers, students	- Perceived reasons and challenges that hinder FA training in schools.

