3.5 SAMPLE SIZE AND SAMPLING

Sample Size Calculation

For the cross-sectional study and Intervention

Assuming an equal number of control and intervention subjects, a prevalence of the outcome in the controls of 0.5, and a prevalence in the intervention group of 0.75 (an absolute increase of 25%)[17] with a power of 80% and 5% error margin, we calculated the sample size needed using STATA.

Estimated sample sizes for a two-sample proportions test Pearson's chi-squared test using STATA

$H_0: p_2 = p_1$ versus $H_a: p_2 \neq p_1$ Study parameters:

```
alpha = 0.0500
power = 0.8000
delta = 0.2500 (difference)
p1 = 0.5000
p2 = 0.7500
```

Estimated sample sizes:

N =	116
N per group =	58

If we assume a 15% drop out rate, we have a sample size of $15\% * 116 = 17.4$ Thus, sample size is $116 + 17.4 = 133.4 \approx 134$

For each group, the sample needed is therefore **N = 67 students. Sampling**

Since this is a crisis area, we will use convenience sampling to choose the Health Areas (HAs) that are secure and geographically accessible (safest) in both HDs. Out of seven (7) and eight (8) HAs in Buea and Tiko HDs respectively, there are 4 accessible HAs in each. Of these, one HA from each HD does not harbour a state secondary school (SSS).

Leaving us with 3 HAs to work with in each HD. Each of these HAs contains 1 SSS but for 1 HA from each District which has 2 SSSs. We would work with all these State schools to ensure that we get students from most of the communities around the schools, thus ensuring the representativeness of our samples. To avoid spill-over, one of the districts will be selected as intervention HD and the other as the control.

Stratified random sampling will be used to select the students for the study from a sampling frame of the list of students in each classroom concerned.

We would use probability proportionate to size to choose the specific number of students to participate in the study per classroom (A, B, and C) for each class.

[figure not shown]

Figure 5: Selection of HAs and Schools for Implementation.

*GHS-Government High School; BGS-Bilingual Grammar School; GTHS Government Technical High School; GBHS government Bilingual High School

For each school distribution of the participants will be as follows:

A) For the Qualitative part:

The qualitative part will be sampled purposively.

Table 2: Number of Participants to be chosen per school for the FGDs

Health District	Schools	FGD Category of Participant	Number per school

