3.7 STUDY VARIABLES AND TYPE

Variables

Outcome variables

1. Knowledge Change: to determine whether or not there was an overall change in knowledge before and after the training (dichotomous).
2. Test scores: to measure the educational efficacy of the first aid training before and after the intervention in comparison with the control group (continuous)
3. Self-efficacy ratings: Participants' self-perceived efficacy in performing first aid skills or their confidence levels in "Stopping the bleed and/or calling for help" (dichotomous)

4. Response time: The time taken by participants to respond to simulated first-aid scenarios or emergencies that require them to either stop an LTB or call for help or refer (continuous).
5. The number of participants who make use of the skills taught during the 3 months post-training but before the final assessment (Discrete).

Exposure Variables

The exposure variables include training on LTBs from injury first aid and the use of these services by the trained students (e.g., the number of persons assisted or referred during the follow up period of the training).

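### The 80% power in section 3.5 is for a one-time comparison of two proportions and does not carry over to the difference-in-difference named in section 3.11

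*Protocol*

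**What the plan says.** Section 3.5 covers both the survey and the intervention with one calculation, introduced as "Estimated sample sizes for a two-sample proportions test Pearson's chi-squared test using STATA". Its inputs are two-sided alpha 0.05, power 0.80, proportions of 0.50 and 0.75 ("delta = 0.2500 (difference") and equal groups. It gives 58 per group, raised to 67 for 15% dropout; Table 5 plans 70 per arm. The section does not say which outcome the 50% and 75% describe. It gives no baseline proportion, no expected change in controls and no pre/post correlation.

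Section 3.11 opens with "A difference-in-difference analysis would be done to assess the change in KAPs before and after the intervention in" (the sentence breaks off there). It then adds, in general terms, parametric and non-parametric tests between pre- and post-test results and between the two groups.

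Section 3.7 lists candidate outcomes of both kinds. One is "Knowledge Change: to determine whether or not there was an overall change in knowledge before and after the training (dichotomous"). Another is "Test scores: to measure the educational efficacy of the first aid training before and after the intervention in comparison with the control group (continuous"). Table 7 gives the change in knowledge scores as an indicator for the effectiveness objective. Section 3.12 says that tests carry initials, so each pupil's pre- and post-tests can be linked.

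**The concern.** A post-only comparison of two proportions carries the sampling error of two measurements, one per arm. A difference-in-difference subtracts each arm's baseline and so carries the error of four, partly offset by the correlation between a pupil's two tests. At equal sample size its power falls short of the post-only test unless that correlation is about 0.5 or more. Section 3.5 does not mention the correlation, so nothing in the protocol connects the 80% to the one method that section 3.11 names for change in KAPs.

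The contrast matters here because districts, not pupils, are assigned to training or control. Baseline differences between the arms are therefore plausible, and the difference-in-difference is the planned analysis that removes them. Chapter Four intends the results to inform scale-up and policy. A null difference-in-difference read against a claimed 80% could be taken as evidence that training does not work, when the contrast may have had considerably less power.

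**Working it through.** **1. The plan's own figure.** Inputs from section 3.5: p1 = 0.50, p2 = 0.75, two-sided alpha 0.05, power 0.80. With pooled proportion 0.625:

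n = [1.96·√(2·0.625·0.375) + 0.8416·√(0.25 + 0.1875)]² / 0.25² = (1.3419 + 0.5567)² / 0.0625 = 57.7, so 58 per group.

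Power at 58 is 80.2%. The figure reproduces (two-sided, no continuity correction).

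**2. Difference-in-difference on the same binary scale.** Assumptions that are not in the protocol: both arms start at 0.50, controls stay at 0.50, trained pupils rise to 0.75, and the within-pupil pre/post correlation is r. The effect is still 0.25.

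- Control arm variance of change: 0.25 + 0.25 − 2r·0.25 = 0.5 − 0.5r
- Trained arm variance of change: 0.25 + 0.1875 − 2r·√(0.25·0.1875) = 0.4375 − 0.4330r
- SE = √(sum of the two / n); power = Φ(0.25/SE − 1.96)

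| r | SE (n = 58) | 0.25/SE | Power, 58 per group | Power, 70 per group |
|---|---|---|---|---|
| 0 | 0.1271 | 1.966 | 50% | 58% |
| 0.3 | 0.1065 | 2.348 | 65% | 73% |
| 0.5 | 0.0901 | 2.774 | 79% | 86% |

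At 58 per group power reaches 80.0% at r = 0.51. At 70 per group, meaning nobody drops out, it is 79.5% at r = 0.4. Simulation of paired binary data (20,000 runs per setting) gave 49.6%, 64.4% and 79.4% at 58 per group, in agreement.

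With proportions of 0.50 and 0.75 the largest possible correlation in the trained arm is √(0.5·0.25 / (0.5·0.75)) = 0.577. At 58 per group, only correlations from about 0.51 to 0.58 give 80% on the binary scale.

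**3. Sensitivity to the assumed baseline.** Suppose instead that both arms start at 20%, controls reach 50% and trained pupils 75%. At r = 0 the variances are 0.16 + 0.25 = 0.41 and 0.16 + 0.1875 = 0.3475. SE = √(0.7575/58) = 0.1143, and power is 59%. The shortfall remains, but its size moves with the baseline.

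**4. Difference-in-difference on the continuous test score.** For a shift of d standard deviations, SE = √(4(1 − r)/58), which is 0.2349 at r = 0.2 and 0.1857 at r = 0.5. The protocol gives no d, so two values are shown.

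- d = 0.52, the shift that 58 per group detects with 80% power in a post-only test (2.8016·√(2/58) = 0.520): power is about 60% at r = 0.2 and 80% at r = 0.5.
- d = 0.67, the 50% versus 75% effect converted by assuming normal scores and a cut at the control median: power is about 81% and 95%.

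The normal approximation and the t distribution agree within about one percentage point. None of the figures in steps 1 to 4 allows for clustering or for one school per arm (Table 5).

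**The case against.** The strongest reply is that section 3.11 does not stop at the difference-in-difference. It also plans tests between the intervention and control groups, and section 3.7 lists a dichotomous knowledge-change outcome for which the share of pupils who improved could be compared once between arms. The section 3.5 calculation fits that test exactly. This stands. A reader might infer that the 80% is wrong however the plan is read, and the documents do not support that. The fault is narrower: the powered outcome and contrast are not named, and the stated power does not belong to the only method named for change in KAPs.

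It can also be said that the 50% to 79% range comes from assumed inputs. This stands too. The equal 50% baselines, flat controls and correlations from 0 to 0.5 are not protocol figures. Hypothesis 2 expects limited baseline knowledge, and zero correlation is unlikely when the same pupils repeat the same questionnaire. Enrolling 70 also helps if few drop out, although 15% dropout from 70 leaves 59 or 60, and power is then almost the same as at 58 (51–52%, 66–67% and 80–81% at correlations 0, 0.3 and 0.5).

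Finally, some of this detail could sit in a statistical analysis plan. But the protocol itself states both the test behind the 80% and a different named analysis, so the mismatch lies in the protocol.

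**Conclusion.** The point holds in limited form. The 80% in section 3.5 is correct for one between-arm comparison of 50% with 75% and is not the power of the difference-in-difference in section 3.11. With 50% baselines, flat controls, 58 analysed per group and no clustering, the latter has about 50% to 79% power for correlations from 0 to 0.5. It reaches 80% at about 0.51, or at about 0.4 with all 70 analysed.

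Two stronger conclusions are tempting and not supported. One is that the study is underpowered as a matter of fact: that depends on a correlation and a baseline that the protocol does not give. The other is that moving to the continuous score secures adequate power with the same pupils. That depends on the effect size (about 60% or about 81% at correlation 0.2, for 0.52 or 0.67 SD). With one school per arm, school-specific change over time cannot be separated from the effect of training, and none of these figures reflects that.

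**What to change.** In sections 3.5 and 3.11, name one powered outcome and one contrast, and make the power statement match. Either of two routes would do:

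- Keep the present calculation. Name the dichotomous outcome that it concerns, and state that the 80% applies to a single between-arm comparison of that outcome and not to the difference-in-difference.
- Restate the power for the difference-in-difference, on the binary outcome or on the continuous test score already collected. Give it as a range over declared baseline, effect-size and pre/post correlation assumptions. For the continuous score, show more than one effect size, as in step 4 of the working, and not a single favourable figure.

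In both cases, say that the figures exclude the effect of having one school per arm.

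The cost is protocol wording and one recalculation. No change in the number of pupils is needed to correct the statement, but the stated power may become less favourable.

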3.12 ETHICAL CONSIDERATIONS

This research will prioritize the ethical principles of informed consent, confidentiality, and respect for participants. All participants will be informed about the purpose of the study and their right to withdraw at any time. Parental consent will also be obtained from the students before carrying on with the trainings. Confidentiality of information obtained from participants will be strictly maintained, and ethical approval will be sought from the institutional review board of the Faculty of Health Sciences of the University of Buea.

NB: Following the research study, all the children within the various schools will be retrained on the program to ensure equity.

Potential risks and Mitigation Strategies

Risks	Mitigation Strategies
Breach in confidentiality	No names on the pre and post-tests, only initials to be able to measure the degree of KAP change, no other potential respondent will come in contact with the filled questionnaires
Loss of time	-The tests are administered by data collectors using filling will be faster Duration: 30mins only. -For the qualitative part, the participants will be informed ahead of time so that their convenience is met.
Psychologic risks related to filling of the questionnaires or taking tests and responding.	Questions in the tests will be simply focused on what will/has been taught and in very simple languages with explanations given to the entire group at once if clarifications needed. Respondents will be counselled prior to the interviews and be given liberty to back out at any moment.
Difficulty interacting during interviews since some people are not used to being recorded.	Interviews will be performed at convenience of the interviewee. The interviewees will also be allowed to ask questions and the research team will answer all questions in line with the study.

Potential Benefits

For the Participants:

- They will be first in the secondary schools in the Southwest to benefit from such knowledge and skill set.
- They will have the opportunity to apply the knowledge and skills learnt among their peers and the communities where they live.
- They shall each benefit from a transport for the evaluation phase.

The population:

- They shall be the first to benefit from such services in the advent of traumatic injuries and these will be free of charge.
- They will contribute ideas to help improve on the YoFA program.

The country:

- The educational and health systems can leverage on this program to build a comprehensive FA curriculum for schools and other institution to raise a FA culture and alleviate adverse outcomes of traumatic injuries.

Measures taken for data confidentiality and respect for the private lives of the participants

- There are no names on the questionnaires, and no other parents will have access to the questionnaires.
- Questions posed will solely be related to the study.
- We will use codes to input and analyse the data and only the data managers (2) will have full access to the coded file where data is managed.

- Informed and parental consent will be obtained from participants prior to the study
- Informed consent will be obtained from interviewees in person before the interview.
- Administrative approval will be obtained from the various schools, regional delegations, and districts and ethical clearance from the ethical committee of the University of Buea.

CHAPTER FOUR

EXPECTED RESULTS

Overall, we expect to be able to determine perceptions of stakeholders regarding introducing a YoFA training program in early secondary schools, determine effectiveness of the program and usability of the skills taught, as well as identify challenges in implementing the program. The study will equally help us to reasonably and measurably improve KAP of early SSC on injury and trauma first aid basics, particularly in life threatening bleeds. We equally hope to determine the outcomes of this intervention and propose solutions as to how we can overcome the barriers identified.

The results will inform policymakers, educators, and healthcare professionals about the need for targeted interventions in first-aid training programs in schools. Additionally, the study will contribute to the existing literature on first aid training in low-resource settings, particularly focusing on the Sub-Saharan African context.

The expected results will be used to determine the scalability of the intervention and its incorporation into public health and educational policies in Cameroon to foster intersectoral collaboration and overall, lower morbidity and mortality from injury/trauma events.

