3.6 STUDY PROCEDURE

The study will use the precede proceed planning model and the ecological model described in the review of Literature following the steps below from planning the research project, through implementing the intervention, and to the monitoring and Evaluation phases.

Step 1: Preparatory/Planning Phase

The planning model to use here will be the Ecological model in conjunction with aspects of the PRECEDE-PROCEED planning model (PPPM).

The other steps of the planning phase include:

- Preparing documents to apply for ethical clearance and administrative authorizations to perform the study.
- Authorizations are needed from the Regional Delegation of Secondary Education for the SWR (1), the divisional delegates/inspectors of the aforementioned ministry (2), the School Principals (8) the Regional Delegation of Public Health

(RDPH) for the SWR (1), and the Chiefs of Health Districts (CHDs) (2)

- Constitute and train a team of 4 trainers medical doctors/students and data collectors and interviewers.
- Obtain a sample frame of students from the various classrooms of the various schools and proceed with the selection of participants as described above.
- Enlist all potential teachers and stakeholders to be interviewed

Step 2: Intervention Phase

- Organize students to be trained in groups of 10.
- Each training session will last 2.5 hours and each group will be trained for 2 days.

That is a total of 5 hours.

- Overall, it will take 6 weeks (1 month, 2 weeks) to train 3 groups of 25 students each as shown in *Table 6* below.
- The Sessions will begin with a 30-to-45-minute pretest followed by theory on day 1. Then mixed theory, video, and practical sessions on days 1 and 2. Main contents Content include: 1. responding to emergencies (first aid) and on prevention of injuries: “Call for help”, fever and contents of a first aid kit, 2. controlling Life-threatening bleeds (LTBs) and immediate first aid in burn cases, fractures, and/or dislocations in the face of LTB [11,46]. It will include the use of cartoons, simple language and memory aids:

(1) Video, (2) small group teaching, (3) demonstration manikin, (4) supervised practice.

- Interviewing the teachers, principals and other stakeholders. Interviews will be done using interview guides and tape recorders.
- For the control group, we will do a selection of the participants as described and there

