will be a session for pretesting at the beginning of the intervention, at the immediate end, and 3 months after. **During the 3 months follow up period, we will visit the schools during their Wednesday club days every 2 weeks for 30mins to 1hour, to document their experiences and challenges in real time and their use of the skills.**

The qualitative part will take place before the quantitative pretesting of both groups begins.

Table 6: Plan of training and Evaluation of intervention groups

HA	School	N	Training Period in 2024	Date for Last Evaluation, 2024
Molyko (Intervention)	BGS Molyko	25	Nov 6 th , and 13 th	Feb 5 th
		25	Nov 20 th , and 27 th	Feb 19 th
		25	Dec 4 th and 11th	March 5 th
Mutengene (Control)	GHS Mutengene	70	November 6 th	Feb 26 th
	Total	145		

Step 3: Evaluation Phase

This comprises the evaluation of students' perceptions, barriers, and challenges in learning and applying the skills and lessons learned. It will equally involve evaluating parents' and stakeholders' perceptions about the program and including FA training in school curricula. It will involve the use of evaluation forms. This will take place about the same time as the post-three-month evaluation.

Knowledge will be assessed by evaluating whether the participants have ever heard of first aid or observed situations in which first aid was needed. They will be expected to have an increase in knowledge of first aid, especially regarding calling for help, stopping acute and life-threatening bleeds (LTB), and referrals after the training.

Before the training, we expect people not to have practiced first acts ever or to have

done it in a wrong way or to be scared to carry out specific first aid acts. After the training, we expect them to be more alert and identify situations needing first aid acts. Additionally, we expect their self-efficacy and confidence to perform first aid acts to increase and to effectively carry out first aid acts within their community or the school premises that will be documented using designed forms.

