3.8 DATA COLLECTION TOOLS

A) Questionnaire

**Pre- and Post-Implementation of a Young First Aiders (YoFA) Training
Program Amongst Early Secondary School Children on Injury and Trauma
First Aid in Fako Division.**

Health District _____
Secondary School _____

Date: _____
Class: _____

A) QUESTIONNAIRE

Section 1

Please answer the questions below by **ENCIRCLING OR WRITING** the right answer you think is correct. If you do not know an answer, please select the answer you think is correct.

1. Gender	YES	or	NO
2. Age (in years):	_____		
3. Parents' Occupation:	Father _____ Mother _____		
4. Do you have access to a mobile phone all the time?	YES	or	NO
5. Have you heard the words First Aid?	YES	or	NO
6. Have you ever seen a traumatic injury? (A traumatic injury is an injury you sustain when something outside your body causes you to lose function or render you unable to use part or all of your body because of pain, bleeding or the because it is very serious)	YES	or	NO
7. A) Have you ever received any training in First Aid (formal or informal)?	YES	or	NO
B) If yes, briefly describe the training (where was it, what did you learn? How long ago was it?)			
Where? _____			
How long ago?			

 a) < 6months ago b) 6 to less than 12 months ago c) 1 to 3 years ago d) >3 years ago 			
What you learnt? _____			
<hr/>			
8. Have you ever seen someone bleeding and tried to stop that bleed yourself at home, school, marketplace, or anywhere else?	YES	or	NO
B) How many times has that happened? (Choose one)			

 a) Never b) Just once c) 2 to 5 times d) >5 times 			

C) What did you do to stop the bleeding? _____ **YES** or **NO**

D) Did it work? **YES** or **NO**

9. **A) Do you remember watching other people do this in the past?** **YES** or **NO**
B) Have you ever watched someone else offer such help in question 5? **YES** or **NO**

10. **If you find someone bleeding today,** **YES** or **NO**

A) Will you help them?

B) If 'no', why will you not help?

- I don't know what to do
- I am afraid I will make it worse
- I am afraid I will get into trouble
- I am afraid of blood
- Other reason _____

C) If 'yes', why will you help? _____

D) What steps will you take to help if 'yes'?

- Help by putting in toothpaste
- Help by applying pressure on the wound
- I will not help
- I will call an elderly person.

[figure not shown]
B) If you would not help, what makes you not want to help?

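### Initials are the stated key for linking each pupil's three tests; they need not be unique, and the protocol does not say that its data codes are on the tests (minor, nearly free to fix)

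*Protocol*

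**What the plan says.** - Section 3.12, risk table, gives both the identifier and its purpose: "No names on the pre and post-tests, only initials to be able to measure the degree of KAP change". The confidentiality list in the same section repeats: "There are no names on the questionnaires".
- Codes appear in two places. Section 3.12 states "We will use codes to input and analyse the data", with full access to the coded file limited to two data managers. Section 3.10 has data collected in Kobo, "then stored in coded excel sheets to be analyzed using R software".
- The questionnaire in 3.8 has fields for health district, school, date, class, gender, age and "Parents' Occupation" (father and mother). It has no study-number field.
- Pupils are tested three times. For controls, section 3.6 says there "will be a session for pretesting at the beginning of the intervention, at the immediate end, and 3 months after". Table 6 puts 70 controls at one school with a single starting date, and 75 trained pupils at one school in three groups of 25.
- Class lists will exist. The planning step in 3.6 is to "Obtain a sample frame of students from the various classrooms of the various schools".
- Section 3.7 lists knowledge change before and after training as a dichotomous outcome. Section 3.11 plans a difference-in-difference analysis and tests of pre- against post-test results, without saying whether those tests are paired.

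**The concern.** Section 3.12 makes initials the means of measuring change, so they have to identify one pupil within the pool in which forms are matched. Two pupils in a class can share initials. A code assigned when a paper form is entered does not solve this, because whoever assigns it must still decide which of two identically initialled pretests belongs to which post-test.

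Three uses depend on a correct link:

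- the dichotomous knowledge change, if it is scored per pupil;
- any pre/post comparison run as paired, through its standard error;
- finding the right pretest for a pupil who is excluded for a missed session or withdraws (3.4.2), or drops out (15% assumed in 3.5).

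Forms completed without a unique identifier may not be separable afterwards, so an analysis plan cannot fully repair the problem later.

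**Working it through.** **The plan's own figure.** With p1 = 0.50, p2 = 0.75, two-sided alpha 0.05 and power 0.80 (3.5), the two-proportion formula gives n = [1.960·√(2·0.625·0.375) + 0.842·√(0.25 + 0.1875)]² / 0.25² = 57.7, so 58 per group and 116 in total. Then 116 + 0.15·116 = 133.4, rounded up to 134. This reproduces the protocol and does not involve linkage. The protocol gives no figure on linkage.

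**Inputs.** From Table 6: 70 controls in one pool and three training groups of 25. Everything else is assumed. K is the number of equally likely sets of initials: 26³ = 17,576 for three letters, 26² = 676 for two, and 150 for two letters with uneven name frequencies. The protocol does not say how many initials are used.

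**Ties.** Expected pupils sharing initials = n·(1 − (1 − 1/K)^(n−1)). If the forms in a tied set are paired at random, on average one per set is still right, so expected mislinked pupils = n − K·(1 − (1 − 1/K)^n).

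| K | Sharing, of 70 controls | Mislinked, of 70 | Sharing, of 75 trained | Mislinked, of 75 |
|---|---|---|---|---|
| 17,576 | 0.3 | 0.14 | 0.1 | 0.05 |
| 676 | 6.8 | 3.5 | 2.6 | 1.3 |
| 150 | 26 | 13.9 | 11 | 5.7 |

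**Per-pupil errors in controls.** Assume pre/post correlation 0.5, unit variances and no mean change. A true change has variance 2·(1 − 0.5) = 1 and a mislinked change has variance 2. Their covariance is 0.5, so their correlation is 0.5/√2 = 0.354. The chance that their signs differ is arccos(0.354)/π = 0.385. Wrong yes/no changes of 70 are therefore 3.46·0.385 = 1.3 (K = 676) and 13.92·0.385 = 5.4 (K = 150).

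**Arm-level proportion improved.** With no mean change in controls, a correct link and a wrong link both give 50%, so the expected shift is zero. For the trained arm, take 75% truly improved (p2 borrowed for scale), which means a mean change of 0.674 SD. A mislinked pupil then shows improvement with probability Φ(0.674/√2) = 0.683, a fall of 0.067. The shift is (5.70/75)·0.067 = 0.5 percentage point at K = 150 and (1.32/75)·0.067 = 0.1 point at K = 676.

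**Paired standard error in controls.** Re-pairing forms within an arm leaves the mean change untouched; only the estimated standard error grows, by √(1 + mislinked fraction). That gives √(1 + 13.92/70) = 1.095, √(1 + 3.46/70) = 1.024 and √(1 + 0.14/70) = 1.001, so increases of 9.5%, 2.4% and 0.1%.

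**Using other fields.** If parents' occupation were also matched (5 to 20 effective father-mother classes, answered the same way each time), the two-initial K becomes 150·5 = 750 up to 676·20 = 13,520. Pupils sharing fall to 6.2 down to 0.4 of 70, and wrong yes/no changes to about 1.2 down to 0.07.

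**The case against.** The strongest reply is that pupil-level errors largely cancel within an arm. This stands. A shift of about half a point or less is small against the 25-point difference planned in 3.5, and an inflated standard error makes a paired test conservative rather than falsely positive. The control shift is zero only because no mean change was assumed; a practice effect would move it off zero.

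Second, 3.10 describes interviewer-administered capture in Kobo. If data are entered directly, a code used at input might be on the record from the start. This is possible, but the Abstract speaks of self-administered questionnaires and the form in 3.8 asks pupils to encircle or write answers, so the text is unclear.

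Third, other fields and records could break ties: age, parents' occupation, class, the class lists and the data collectors' presence. Class separates pupils if they come from several classrooms, as 3.5 first describes, but little if one classroom is used, as the text above Table 5 says. Gender is printed with yes/no options and may not help. Training groups of 10, also mentioned in 3.6, would make ties rarer. None of these is planned as a matching key, and no rule covers a tie.

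Fourth, identifier allocation is often left to data-management documents. Here, however, the protocol does not leave it open: it states a key, and a weak one.

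A reader might infer that shared initials bias the treatment effect or invalidate the difference-in-difference analysis. The documents do not support that. Arm means at each occasion need no individual link, so with all forms kept the point estimate is the same however forms are paired.

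**Conclusion.** The point holds as a minor one. The wording is clear: 3.12 makes initials the linking key, the form has no study-number field, and neither mention of codes places them on the tests. The consequence is limited to per-pupil knowledge change, the precision of paired pre/post tests, and retrieving the pretest of a pupil who leaves. The main point estimate with all forms kept, and N, are not affected.

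The size cannot be fixed from the documents. It rests on assumed numbers of initials, a pre/post correlation of 0.5, no mean change in controls and random pairing of ties, which is an upper case. On two initials this means 1.3 to 5.4 wrong yes/no changes among 70 controls, about half a percentage point or less on an arm's proportion improved, and a paired standard error in controls 2 to 9.5% too large. On three initials the effect is negligible. Matching on age, class or occupation would reduce it further. The case for acting is that the remedy is nearly free and must be in place before the pretest.

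**What to change.** In 3.12, replace the initials-only rule with a unique study number assigned at enrolment and entered on the pretest, immediate post-test and 3-month test, whether on paper or in Kobo. Have the two data managers already named in 3.12 hold the list linking names to numbers, separately from the data. State that this number is the code meant in 3.10 and in the confidentiality measures of 3.12, and add the field to the form in 3.8.

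If a unique code on every test is already intended, correcting the initials wording and saying so is enough.

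Cost: one form field and one list. Sample size, visits and staff are unchanged. Confidentiality is not weakened, since a number tells a classmate less than initials do.
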